8.1.6. Repeat Dose (Part B)

- If more than 1 cohort is recruited in order to investigate more than 1 repeat dose then cohort will be added as a covariate. Only Part B data will be analysed for the repeat dose assessments.

Table 7 Overview of Repeat Dose Summaries

Endpoint / Parameter/ Display Type	Untransformed						Log-Transformed							
	Stats Analysis			Summary		Individual		Stats Analysis			Summary		Individual	
	T	F	L	T	F	F	L	T	F	L	T	F	F	L
Repeat Dose														
Dose Accumulation								Y						
Steady State											Y			
Peak to Trough Ratios								Y						

NOTES:

- T = Table, F = Figure, L = Listings, Y = Display generated.
- Stats Analysis = Represents TFL related to any formal statistical analyses (i.e. modelling) conducted.
- Summary = Represents TFL related to any summaries (i.e. descriptive statistics) of the observed raw data.
- Individual = Represents FL related to any displays of individual subject observed raw data.

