
 • The PK parameter will be dose-normalised prior to log_e-transformation by multiplying by reference dose / dose • Dose will be fitted as a fixed effect, subject as a random effect using DDFM=KR. • Separate lines will be fitted for each cohort by including terms for cohort and cohort*log_e(dose). If the slopes are not significantly (p-value<0.05) different from each other, the interaction term will be removed and a single slope estimate obtained. If the slopes are significantly different from each other, a separate slope estimate and associated 90% confidence interval will be reported for each cohort. • The reference dose will be chosen based on the lowest clinically relevant dose over which PK can be adequately described, with each other dose as the test doses in the construction of the ratio $\mu(\text{test})/\mu(\text{reference})$.
Model Checking & Diagnostics

 • Refer to Appendix 8: Model Checking and Diagnostics for Statistical Analyses.
Model Results Presentation

 • Point estimates for the adjusted means on the log_e scale, the mean difference between each dose (test) and the reference dose and associated 90% confidence interval will be constructed using the residual variance. These will not be presented. • The point estimate and confidence interval will then be exponentially back-transformed to allow the presentation of the adjusted (least square) geometric means for each treatment (dose), and point estimates and associated 90% confidence intervals for the ratio test/reference. • Point estimates and 90% confidence intervals for AUC, C_{max} and C_τ will be reported to 2 decimal places Treatment ratios and 90% CIs will be plotted by dose. • Plots will also be provided showing the adjusted geometric mean ratio of test to reference treatment (dose) for AUC(0-∞), AUC(0-t), C_τ and C_{max} together with 90% confidence interval.

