8.1.6.1. Statistical Analysis of Dose Accumulation and Steady State

The following pharmacokinetic statistical analyses will only be performed, if sufficient data are available (i.e. if subjects have well defined plasma profiles).

Pharmacokinetic Statistical Analyses
Endpoint(s)

 • Dose Accumulation: AUC(0-24), C_τ, C_{max} on Day 14 compared to Day 1 • Each endpoint to be assessed separately following a log-transformation.
Model Specification

 • A mixed effect model will be fitted with day as a fixed effect and subject as a random effect. • The Kenward & Roger (KR) degrees of freedom approach will be used. • Day 14 will be compared to Day 1 in order to estimate the accumulation ratio(s) • The accumulation ratio(s) and 90% confidence interval will be calculated by back-transforming the difference between the least square means for the two days and associated 90% confidence interval.
Model Checking & Diagnostics

 • Refer to Appendix 8: Model Checking and Diagnostics for Statistical Analyses.
Model Results Presentation

 • Point estimates and confidence intervals for the ratios will be reported to 2 decimal places • Scatter plots of each endpoint against day will be produced. The data points for each subject will be joined with straight lines. If there is more than 1 cohort each treatment will be put on a separate page. • Boxplots of each endpoint against day will be produced. If there is more than 1 cohort each treatment will be put on a separate page.

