8.1.6.2. Statistical Analysis of Peak to Trough Ratio

Pharmacokinetic Statistical Analyses
Endpoint(s)

 Peak to trough ratio: Cmax/Ctrough.
Model Specification

 A mixed effect model will be fitted with day*parameter as a fixed effect and subject as a random effect. The Kenward & Roger (KR) degrees of freedom approach will be used. Response variable will be the logged peak concentrations and the logged trough concentrations. Indicator variables will be included to distinguish between the peak and trough concentration data. The differences in lsmmeans of the peak and trough concentrations on each day will be back-transformed to obtain estimates of the peak to trough ratios on each day.
Model Checking & Diagnostics

 Refer to Appendix 8: Model Checking and Diagnostics for Statistical Analyses.
Model Results Presentation

 Peak to trough ratios will be tabulated displaying the adjusted mean (and 90% CIs) Cmax and Ctrough values together with the ratios and corresponding 90% CIs.

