10.4. Appendix 4: Data Display Standards & Handling Conventions

10.4.1. Study Treatment & Sub-group Display Descriptors

Treatment Group Descriptions			
RandAll NG		Data Displays for Reporting	
Code	Description	Description ^[2]	Order ^[1]
A	Placebo inhaled single dose	Placebo	1
B	50ug GSK2292767 inhaled single dose	50ug OD	2
C	Dose Level 2 GSK2292767 inhaled single dose	100ug OD	3
D	Dose Level 3 GSK2292767 inhaled single dose	200ug OD	4
E	Dose Level 4 GSK2292767 inhaled single dose	500ug OD	5
F	Dose Level 5 GSK2292767 inhaled single dose	1000ug OD	6
G	Dose Level 6 GSK2292767 inhaled single dose	2000ug OD	7
H	Placebo inhaled repeat dose	Placebo	1
I	Dose Level 7 GSK2292767 inhaled repeat dose	XXXXug OD	2

NOTES:

1. Order represents treatments being presented in TFL, as appropriate.
2. Replace X's with the actual agreed dose for the cohort and period.

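### If Part B recruits a second repeat-dose cohort, adding cohort only as a covariate gives ratios pooled over doses and no model-based ratio or 90% CI for each dose

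*SAP*

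**What the plan says.** Section 8.1.6 of the SAP sets the rule for all Part B repeat-dose analyses: "If more than 1 cohort is recruited in order to investigate more than 1 repeat dose then cohort will be added as a covariate".

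The accumulation model in 8.1.6.1 is then: "A mixed effect model will be fitted with day as a fixed effect and subject as a random effect". The ratio and its interval come from "back-transforming the difference between the least square means for the two days and associated 90% confidence interval". For peak to trough, 8.1.6.2 says: "A mixed effect model will be fitted with day*parameter as a fixed effect and subject as a random effect", with differences between peak and trough LS means taken on each day. Neither section names a cohort interaction, an LS mean by cohort or a ratio by dose. Table 3.204, which reports both sets of ratios, carries no by-cohort instruction.

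The displays are split. For the accumulation scatter plots and box plots, 8.1.6.1 says: "If there is more than 1 cohort each treatment will be put on a separate page". Figure 3.201 also allows for one cohort per page.

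Section 10.4.1 currently lists one active repeat-dose level, "Dose Level 7 GSK2292767 inhaled repeat dose", so the multi-cohort rule is a contingency.

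**The concern.** The sentence in 8.1.6 exists to deal with a second dose, but the term that it adds cannot do so. Both Part B analyses are within-subject contrasts: Day 14 against Day 1, and peak against trough on the same day. A term that takes one value per subject adjusts the level of a cohort's concentrations. It does not let the contrast differ between cohorts.

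A second dose would be run to learn about that dose, yet the table would hold one ratio for both. If accumulation depends on dose, that ratio lies between the two true values, at a point set partly by the cohort sizes, and its interval is centred away from each of them.

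**Working it through.** The SAP states no figure on this point, so there is none to reproduce.

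**Step 1: the algebra.** With cohort as a covariate, for subject *i* in cohort *c* on day *d*:

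log Y = intercept + day(*d*) + cohort(*c*) + subject(*i*) + error.

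Subtracting Day 1 from Day 14 within a subject removes cohort(*c*) and subject(*i*) and leaves day(14) − day(1), the same quantity in both cohorts. The difference between the two day LS means is this single coefficient, however the LS means weight the cohorts. In 8.1.6.2 the contrast is log peak minus log trough within subject and day, so the cohort term cancels in the same way.

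With incomplete pairs the cohort term can shift the estimate slightly, but the model still holds only one ratio.

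**Step 2: fitted models.** Two-cohort data were simulated and REML mixed models fitted, with 100 runs per scenario. Assumptions, none from the SAP: between-subject log SD 0.40, within-subject log SD 0.25, 6 to 12 subjects per cohort. With complete pairs, adding cohort changed the ratio by at most about 1e-14. The expected pooled ratio with cohort sizes n1 and n2 and true ratios R1 and R2 is exp[(n1 ln R1 + n2 ln R2)/(n1 + n2)].

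| Subjects | True ratios | Expected pooled | Fitted with cohort covariate | Fitted with cohort-by-day |
|---|---|---|---|---|
| 9 / 9 | 1.5, 3.0 | √(1.5 × 3.0) = 2.12 | 2.09 | 1.47, 2.98 |
| 12 / 6 | 1.5, 3.0 | 1.89 | 1.89 | 1.50, 2.98 |
| 6 / 12 | 1.5, 3.0 | 2.38 | 2.41 | 1.53, 3.03 |
| 9 / 9 | 2.0, 2.0 | 2.00 | 2.01 | 1.99, 2.03 |

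When the true ratios differ, the pooled value matches neither dose and moves with the cohort sizes. When they are equal, it is correct.

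**Step 3: coverage of the 90% CI.** With complete pairs the analysis reduces to a t-interval on the paired log differences, whose SD is 0.3 × √2 = 0.42 for an assumed within-subject log SD of 0.3. Cohorts are of equal size, 6 to 9 subjects each (assumed). Simulated coverage of a given cohort's true ratio:

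| True ratios | Pooled ratio | Coverage, 6 per cohort | Coverage, 9 per cohort |
|---|---|---|---|
| equal | common value | 90% | 90% |
| 1.5, 1.65 | √(1.5 × 1.65) = 1.57 | 88% | 87% |
| 1.5, 1.8 | √(1.5 × 1.8) = 1.64 | 83% | 78% to 79% |
| 1.5, 2.5 | √(1.5 × 2.5) = 1.94 | 50% | 31% |

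Coverage falls as the cohorts grow, because the interval narrows around the pooled value. With cohort-by-day fitted, coverage is 90% in every row.

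**Step 4: comparison with Part A.** In 8.1.5.1 the SAP writes out a cohort term and a cohort-by-log-dose term, and says when cohort-specific slopes with 90% CIs are reported. Sections 8.1.6 to 8.1.6.2 contain no counterpart.

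**The case against.** Several objections have force.

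- **It is doubly conditional.** The SAP synopsis plans one dose for Part B, the highest well tolerated in Part A, and 10.4.1 lists one active repeat-dose level. Harm needs a second cohort and dose-dependent accumulation. This stands, and it fixes the low priority.
- **A common ratio can be a reasonable choice** in a small, secondary, estimation-only analysis, and Part A itself drops a non-significant interaction. This stands as an argument for pooling after a stated assumption or check. The SAP gives neither for Part B.
- **The optional plural on the accumulation ratio in 8.1.6.1 may mean one per cohort.** It may equally mean one for each of the three endpoints. The contrast that is specified is a single difference between two day means, and a main-effects model has no cohort-specific ratio to report. This makes the text loose; it does not close the gap.

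Two stronger readings are tempting. A reader might infer that the plan would give no information on accumulation at each dose. It would: the accumulation plots are split by treatment, and Listing 66 gives individual accumulation and peak-to-trough values. Only the model-based ratio and its CI per dose are missing. A reader might also infer that the pooled CI would cover neither true ratio. That is wrong as a general statement: even with true ratios of 1.5 and 2.5, under the assumptions of step 3, the interval misses both in only about 14% of trials with 6 per cohort and about 40% with 9.

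**Conclusion.** The concern holds in conditional form. If a second repeat-dose cohort is recruited, the covariate rule in 8.1.6 does nothing to the accumulation or peak-to-trough contrasts with complete data, and no model-based ratio or 90% CI is produced for each dose.

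That the contrast is unchanged follows from the SAP's own model and needs no assumed figures. The size of the harm does depend on assumptions: it runs from none if the doses accumulate equally, through a modest loss of coverage for 1.5 against 1.8, to a serious loss for 1.5 against 2.5. The SAP gives no true ratios, within-subject SD or cohort sizes with which to choose among these, and coverage was simulated for accumulation only. The planned single-dose Part B is unaffected. This is a small but worthwhile clarification of a secondary analysis.

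**What to change.** Replace the sentence in 8.1.6 with: *If more than one cohort is recruited, cohort and cohort\*day (for peak to trough, cohort\*day\*parameter) will be fitted and ratios with 90% CIs reported per cohort; a pooled ratio may be given in addition.* Add a matching note to Table 3.204.

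If the sponsor prefers a common ratio, the alternative is to state that assumption, justify it and say how it will be checked. Either change should be made before database freeze, the SAP's own deadline for decisions on the final analysis.

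The cost is one sentence and some precision. In the simulations of step 3, per-cohort intervals were wider than the pooled one on the log scale by a factor of about 1.2 for true ratios 1.5 and 2.5, and about 1.4 if the ratios are equal (close to √2, since each cohort has half the subjects). Nothing changes if only one cohort is run.

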8.1.6.1. Statistical Analysis of Dose Accumulation and Steady State

The following pharmacokinetic statistical analyses will only be performed, if sufficient data are available (i.e. if subjects have well defined plasma profiles).

Pharmacokinetic Statistical Analyses
Endpoint(s)

 • Dose Accumulation: AUC(0-24), C_τ, C_{max} on Day 14 compared to Day 1 • Each endpoint to be assessed separately following a log-transformation.
Model Specification

 • A mixed effect model will be fitted with day as a fixed effect and subject as a random effect. • The Kenward & Roger (KR) degrees of freedom approach will be used. • Day 14 will be compared to Day 1 in order to estimate the accumulation ratio(s) • The accumulation ratio(s) and 90% confidence interval will be calculated by back-transforming the difference between the least square means for the two days and associated 90% confidence interval.
Model Checking & Diagnostics

 • Refer to Appendix 8: Model Checking and Diagnostics for Statistical Analyses.
Model Results Presentation

 • Point estimates and confidence intervals for the ratios will be reported to 2 decimal places • Scatter plots of each endpoint against day will be produced. The data points for each subject will be joined with straight lines. If there is more than 1 cohort each treatment will be put on a separate page. • Boxplots of each endpoint against day will be produced. If there is more than 1 cohort each treatment will be put on a separate page.

8.1.6.2. Statistical Analysis of Peak to Trough Ratio

Pharmacokinetic Statistical Analyses
Endpoint(s)

 Peak to trough ratio: Cmax/Ctrough.
Model Specification

 A mixed effect model will be fitted with day*parameter as a fixed effect and subject as a random effect. The Kenward & Roger (KR) degrees of freedom approach will be used. Response variable will be the logged peak concentrations and the logged trough concentrations. Indicator variables will be included to distinguish between the peak and trough concentration data. The differences in lsmmeans of the peak and trough concentrations on each day will be back-transformed to obtain estimates of the peak to trough ratios on each day.
Model Checking & Diagnostics

 Refer to Appendix 8: Model Checking and Diagnostics for Statistical Analyses.
Model Results Presentation

 Peak to trough ratios will be tabulated displaying the adjusted mean (and 90% CIs) Cmax and Ctrough values together with the ratios and corresponding 90% CIs.

8.1.7. Population Pharmacokinetic Analyses

A PME/MAP compliant file will be generated for this study to enable population PK model development, if possible (dependent on data). Data from subjects from both study parts (Parts A and B) will be provided in this file, even for subjects who may not have received a full dose. Such subjects may be included in any subsequent POP PK analysis.

An example file structure is provided in the attachments in Section 10.11. The PME/MAP compliant file will be produced by or under the auspices of Clinical Statistics (Programming).

8.2. Pharmacodynamic Analyses (Parts A and B)

8.2.1. Overview of Planned Pharmacodynamic Analyses

Analyses will be performed separately for each study part.

The pharmacodynamic analyses will be based on the Safety population, unless otherwise specified.

[Table 8](#) provides an overview of the planned pharmacodynamic analyses, with full details of data displays being presented in [Appendix 11: List of Data Displays](#).

Table 8 Overview of Planned Pharmacodynamic Analyses

Endpoint / Parameter/ Display Type														
	Untransformed							Log-transformed						
	Stats Analysis			Summary		Individual		Stats Analysis			Summary		Individual	
	T	F	L	T	F	F	L	T	F	L	T	F	F	L
Phospholipid Data														
PIP2 peak area				Y			Y				Y		Y	
PIP3 peak area				Y			Y	Y	Y		Y		Y	
PIP3 peak area proportion (of PIP2 peak area and PIP3 peak area)				Y			Y	Y	Y		Y		Y	

NOTES:

- T = Table, F = Figure, L = Listing, Y = Yes display generated.
- Stats Analysis = Represents TFL related to any formal statistical analyses (i.e. modelling) conducted.
- Summary = Represents TFL related to any summaries (descriptive statistics) of the observed raw data.
- Individual = Represents FL related to any displays of individual subject observed raw data.

8.2.2. Planned Pharmacodynamic Statistical Analyses

Planned Statistical Analyses
Endpoint(s)

 • PIP3 Peak Area proportion (calculated as a proportion of the sum of PIP2 Peak Area and PIP3 Peak Area i.e. $\text{PIP3 Peak Area} / (\text{PIP2 Peak Area} + \text{PIP3 Peak Area})$)
Model Specification

 • Repeated measures analysis based on the two replicates for each subject on each study day. • Replicates are to be modeled using VC (variance components) structure • Response variable: $\text{Loge}(\text{PIP3 Peak Area proportion})$. The following will be included as fixed effects: Part A: period, treatment*daytime Part B: treatment*daytime*base Where daytime can take the values: Part A: 'Day 1 3h', 'Day 1 24h' Part B: 'Baseline', 'Day 1 3h', 'Day 1 24h', 'Day 12 3h', 'Day 12 24h' • Daytime and subject will be fitted as random effects
Model Checking

 • Refer to Appendix 8: Model Checking and Diagnostics for Statistical Analyses.

Planned Statistical Analyses
Model Results Presentation

• Adjusted geometric means for each treatment group will be presented along with 90% confidence intervals (CIs).• Part A: Point estimates of the treatment differences versus placebo and their associated 90% CIs will be calculated for both timepoints (using the pooled estimate of variance) and back transformed to provide estimates and 90% CIs for the treatment ratios.• Part B: Point estimates of the daytime differences versus placebo and their associated 90% CIs will be calculated (using the pooled estimate of variance) and back transformed to provide estimates and 90% CIs for the treatment ratios at each timepoint.• Bayesian posterior probabilities of seeing differences from placebo less than 0 (ratio less than 1) will be displayed.• Adjusted geometric means (for each treatment group and timepoint) and treatment ratios, along with 90% CIs will be plotted.

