10.5.5. Pharmacodynamic

Sputum Data
PIP3 Ratio

 PIP3 is the analyte of primary interest for the phospholipid data in sputum, and Peak Area data from the mass spectrometer is the endpoint of interest. However, it is acknowledged that there will be some degree of variability between sputum samples due to differences in cell counts, and therefore it is favoured to first normalise PIP3 Peak Area values by (PIP2 Peak Area + PIP3 Peak Area); prior to analysis. More specifically the parameter of interest is: PIP3 Peak Area proportion (calculated as a proportion of the sum of PIP2 Peak Area and PIP3 Peak Area i.e. PIP3 Peak Area / (PIP2 Peak Area + PIP3 Peak Area)). PIP3 Peak Area, as a proportion of PIP2 Peak Area and PIP3 Peak Area, will be used to calculate the PIP3 Peak Area proportion as follows:

Sputum Data
$PIP3 \text{ Peak Area proportion} = \frac{PIP3 \text{ Peak Area}}{PIP2 \text{ Peak Area} + PIP3 \text{ Peak Area}}$ 
 PIP3 peak area, (PIP3) may be standardised by dividing by a PIP3 standard e.g. ISDPIP3. Similarly, PIP2 peak area (PIP2) may be standardised by dividing by a PIP2 standard e.g. D6PIP2. Multiple standards will be included in the PIP dataset. The unstandardised PIP2 and PIP3 peak areas will be used in the derivation of the PIP3 peak area proportion for the SAC outputs. However, the choice of standards to be used in the analysis may be explored e.g. through comparison of distributions, linear regression post SAC.

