10.8. Appendix 8: Model Checking and Diagnostics for Statistical Analyses

10.8.1. Statistical Analysis Assumptions

Endpoint(s)	
 • Dose proportionality, accumulation, peak to trough ratio, PIP3 Ratio
Analysis	
 • Mixed effects models

 • The Kenward and Roger method for approximating the denominator degrees of freedom and correcting for bias in the estimated variance-covariance of the fixed effects will be used. • An unstructured covariance structure for the R matrix will be used by specifying 'type=UN' on the REPEATED line. 
 ○ In the event that this model fails to converge, alternative correlation structures may be considered such as CSH or CS. ○ Akaike's Information Criteria (AIC) will be used to assist with the selection of covariance structure. • Distributional assumptions underlying the model used for analysis will be examined by obtaining a normal probability plot of the residuals and a plot of the residuals versus the fitted values (i.e. checking the normality assumption and constant variance assumption of the model respectively) to gain confidence that the model assumptions are reasonable. • If there are any departures from the distributional assumptions, alternative models will be explored using appropriate transformed data. 	

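### PIP3 replicates: Section 8.2.2 and Appendix 8 prescribe different covariance structures, and the one in 8.2.2 leaves Part A without a sample-level term, so its 90% CIs are too narrow if samples vary

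*SAP*

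**What the plan says.** SAP Section 8.2.2 specifies the PIP3 model as follows.

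- Unit of analysis: "Repeated measures analysis based on the two replicates for each subject on each study day".
- Structure for the replicates: "Replicates are to be modeled using VC (variance components) structure".
- Random effects: "Daytime and subject will be fitted as random effects". No nesting is stated.
- Fixed effects: "Part A: period, treatment*daytime". Part B uses treatment by daytime by baseline.
- Output: ratios to placebo with 90% CIs from the pooled variance, and Bayesian posterior probabilities that the ratio is below 1.

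Section 8.2.2 refers to Appendix 8 for model checking. Section 10.8.1 in that appendix covers these endpoints: "Dose proportionality, accumulation, peak to trough ratio, PIP3 Ratio". For them it says: "An unstructured covariance structure for the R matrix will be used by specifying" type=UN on the REPEATED line. If that model does not converge, "alternative correlation structures may be considered such as CSH or CS", with AIC assisting the choice. VC is not named there, and no blocking factor is given.

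**The concern.** The two sections give different instructions for the same endpoint, and the difference matters. With the sample as the block, UN or CS over the two replicates carries their covariance, and so carries the variance between samples. VC sets that covariance to zero, so any correlation between readings of one sample must come from the random effects.

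In Part A the listed random effects cannot supply it. Each subject has three periods with two sputum times in each, so a sample is one subject by period by daytime combination.

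- A random daytime main effect duplicates the fixed treatment by daytime term and cancels in same-timepoint contrasts.
- Daytime within subject is shared across the three periods, so it does not separate the samples that carry the treatment contrast.

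Under either reading, duplicate assays of one sample are treated as if they were separate samples. At stake are the Part A ratios' 90% CIs and posterior probabilities, which are the trial's inferential evidence of target engagement.

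**Working it through.** **The SAP's own figures.** It gives no PIP3 variance, intraclass correlation or sample size, so there is nothing to reproduce. Everything below rests on labelled assumptions.

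**Set-up.** A log reading is subject + sample (variance s²) + replicate error (variance e²), with two replicates per sample. Let rho = s²/(s² + e²).

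**Step 1, large-sample approximation.** The true within-subject variance of a sample mean is s² + e²/2. Without a sample term the model takes it as about (s² + e²)/2. The ratio of true to model variance is (2s² + e²)/(s² + e²) = 1 + rho, so the SE is too small by a factor of about √(1 + rho). Coverage of the nominal 90% CI is 2Φ(1.645/√(1 + rho)) − 1. At rho 0.5, 1.645/1.225 = 1.343 and coverage is 82%.

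**Step 2, allowing for finite size.** Assume 2 cohorts of 8.

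- There are 16 × 3 × 2 = 96 samples and 192 readings.
- Section 10.4.1 lists placebo and six single-dose levels, so treatment by daytime has 7 × 2 = 14 cells. Adding 2 period terms and 16 subjects, less 1 shared intercept, gives 31 parameters.
- The residual pools 96 − 31 = 65 between-sample degrees of freedom with 96 replicate degrees of freedom, 161 in all.
- Its expectation is [65(2s² + e²) + 96e²]/161 = e² + 0.81s², lower than Step 1 assumed.
- The model-to-true SE ratio becomes √[(1 − (31/161)rho)/(1 + rho)], which is 0.83, 0.78 and 0.66 at rho 0.36, 0.5 and 0.9. Simulated ratios with daytime not nested were 0.82-0.83, 0.77-0.79 and 0.65-0.66 (the last for rho 0.90-0.94).

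**Step 3, REML simulation of Part A.** Fixed effects were period and treatment by daytime. Assumed: 8 per cohort (7 in some runs), several placebo allocations, subject SD 0.3 or 0.5 on the log scale (or subject variance 0.5 against within-subject variance 1), and 120 to 400 runs per setting. Some runs used residual-type degrees of freedom in place of Kenward-Roger.

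Coverage of the nominal 90% CI versus placebo under 8.2.2:

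| rho | Step 1 | Step 2 | Simulated, daytime not nested | Simulated, daytime within subject |
|---|---|---|---|---|
| 0 | 90% | 90% | 89-91% | 89-91% |
| 0.25 | 86% | 85% | 84% | 84% |
| 0.36 | 84% | 83% | 83-84% | 82% |
| 0.50 | 82% | 80% | 79-82% | 79-80% |
| 0.64 | 80% | 77% | 78% | 76% |
| 0.75 | 79% | 75% | 78% | 76% |
| 0.90 (some runs to 0.94) | 77% | 72% | 71-75% | 68-74% |

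With a sample-level term, or one value per sample, simulated coverage was 88-91%.

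**Step 4, posterior probabilities.** Assume a flat prior and the model's own SE; the SAP states neither. A probability that should be 0.90 prints as Φ(1.2816 × √(1 + rho)) = 0.93, 0.94 and 0.96 at rho 0.36, 0.5 and 0.9. Dividing 1.2816 by the Step 2 SE ratios instead gives 0.94, 0.95 and 0.97.

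**Step 5, Part B.** Here subject by daytime is the sample. If daytime is nested in subject there is no loss (simulated 89-91%). If it is not, coverage was 84-88% for rho 0.36 to 0.90. These runs assumed 10 active and 5 placebo subjects and omitted the baseline term of 8.2.2, so they are only a rough guide.

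**The case against.** **Precedence.** Section 8.2.2 is the endpoint-specific model, while Appendix 8 is a shared block on model checking, so a programmer might well follow 8.2.2. The fallback list is also open-ended. This does not resolve the conflict: Appendix 8 names this endpoint, its alternatives apply only if UN fails to converge, and no precedence rule is given. If 8.2.2 does prevail, the narrow intervals follow.

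**Meaning of VC.** Neither section names the block. A diagonal residual is the ordinary reading of VC for replicates, but it is a reading, and the benefit of UN depends on blocking by sample.

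**Evidence that samples vary.** Section 10.5.5 expects "some degree of variability between sputum samples due to differences in cell counts", but gives this as the reason to normalise PIP3 by PIP2 plus PIP3. It is therefore not evidence of variance left in the normalised endpoint. This point stands: rho is unknown, and at rho 0 nothing is lost. Still, the SAP does not claim that normalising removes all variation between samples, and differences between induction occasions are plausible.

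**Figures.** √(1 + rho) understates the simulated effect at high rho; Step 2 of the working accounts for most of the gap. The Part B figures come from a simplified model and carry little weight.

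**Importance.** PIP3 is exploratory. Section 3.1 bases escalation and the Part B dose on safety and PK, and Section 10.6.2 defers the decision on PD analysis until the data are reviewed. This limits the consequences but does not correct the model.

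**Conclusion.** The concern holds. The covariance instructions in Sections 8.2.2 and 10.8.1 conflict for the same endpoint, and the model in 8.2.2 has no sample-level term in Part A under either reading of the random effects. If samples vary beyond replicate error, the Part A CIs are too narrow and the posterior probabilities too extreme. On the assumed designs, nominal 90% coverage falls to about 82-84% at rho 0.36, 79-82% at 0.5 and 68-75% at 0.9. The direction follows from the model; the size depends on a rho that the SAP does not give. Part B is affected only if daytime is not nested in subject. This should be fixed, but it does not threaten the primary safety objective or any dose decision.

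**What to change.** Choose one model for PIP3 and state it in Section 8.2.2:

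- (a) analyse one value per sample, the mean of the two log replicates, with subject random. This matches Tables 4.101 and 4.201, which already summarise the geometric mean of the replicates; or
- (b) keep both replicates with the VC residual and add a random subject by period by daytime effect in Part A and subject by daytime in Part B.

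In either case state how daytime is nested. Amend Section 10.8.1 so that type=UN is not applied to the PIP3 replicates: under (b) the UN covariance is confounded with the sample effect, and under (a) no replicate block is left.

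The cost is a wording change and one model statement, settled before database freeze as the SAP synopsis requires of analysis decisions. Part A intervals widen when samples vary. In the simulations with 8 per cohort and daytime not nested, the 8.2.2 intervals were 0.79 times the sample-level width at rho 0.5, so the corrected ones would be about 1/0.79 = 1.27 times as wide. At rho 0 the width is unchanged.
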